#### 7.3 Data Analysis

Data analysis will be done mostly by dose group and will be exploratory due to the small sample size.

#### 7.3.1 Analysis of the primary endpoints

Baseline descriptive statistics on all evaluable patients will be provided for demographic variables (age, sex, race/ethnicity), ECOG performance status, disease stage and status at the screening and treatment regimens previously used.

The NCI Common Terminology Criteria for Adverse Events, version 4.0 (CTCAE v4.0) will be used to evaluate toxicity. We will consider a toxicity to be an adverse event that is possibly, probably or definitely related to treatment. The maximum grade of toxicity for each category of interest will be recorded for each patient and the summary results will be tabulated by category and grade. We will describe all DLTs and other serious (≥ Grade 3) adverse events on a patient-by-patient basis; descriptions will include dose level and any relevant baseline data. The monitoring and follow-up procedures are listed in detail in section 6.3.1 and 6.3.2. Specifically, patients will be seen at one, two, and three months post SBRT, five months post SBRT, and then every three months thereafter. They will undergo a comprehensive physical exam at each of

these visits. Monthly blood work will also be completed starting 2 weeks following SBRT - CBC, Diff with platelets, basic electrolytes, BUN, creatinine, t-bili, ALT, AST, GGTP, calcium, magnesium, and phosphorus. Bloodwork will be completed and reviewed for at least the first six months. All toxicity data gathered from these visits will be graded according to CTCAE v4.0. Statistics on the radiation dose and number of fractions received by patients will be tabulated.

#### 7.3.2 Analysis of Secondary Endpoints

Local control, local failure, regional failure and distant failure of patients, defined in Section 6.5.1.5, will be summarized in tables. Their rate will be calculated along with their exact 95% confidence intervals. The local response rates with FDG-PET/CT will be compared to those with CT using McNemar's test. The HRQL data analysis will be mostly descriptive and performed according to Section 6.5.1.6.

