A similar phase I trial was conducted at the Princess Margaret Hospital with escalating doses from 27.7 Gy to 60 Gy in six fractions in 70 patients with 143 tumors. The rate of grade III toxicity in this cohort was 10%, manifesting as liver enzyme elevation, thrombocytopenia, and abdominal pain. One paient developed a grade 5 small bowel obstruction. The one year local control was 71%. A study conducted in the Netherlands examined the use of SBRT in the treatment of 45 liver metastases and 11 hepatocellular carcinomas. Patients with metastases were treated to 37.5 Gy over 3 fractions. In the metastases group, the actuarial local control at 1 and 2 years was 100% and 86%, respectively. There were 2 episodes of grade III toxicity manifesting as an incease in GGT. Actuarial 2-year survival was 62% in the metastases group. All of the above data suggest that SBRT is a safe, effective way to deliver non-invasive, local therapy to liver metastases.

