#### 4.3 Inclusion Criteria

All patients must meet the following criteria in order to be included in this study.

- a. Male or female patients  $\geq 18$  years of age
- b. A life expectancy of at least 6 months with a Karnofsky performance status of at least 70 (Appendix IV)
- c. The target lesion(s) can be accurately measured in at least one dimension according to RECIST and must have a maximum tumor volume of  $\leq 100 \text{ cm}^3$ .
- d. No prior radiotherapy to the upper abdomen.
- e. Previous systemic chemotherapy or non-radiation local therapy (such as surgery, hepatic arterial therapy, chemoembolization, radiofrequency ablation, percutaneous ethanol injection or cryoablation) is allowed. The lesion must however have shown criteria of progression based on RECIST. Local therapy must be completed at least 4 weeks prior to the baseline scan. This is to create a safer treatment environment and to help determine the effect of treatment by SBRT alone. Patients will be allowed to go onto appropriate systemic therapy, as determined by their medical oncologist, 2 weeks following delivery of SBRT.
- f. Patients with resectable disease will be eligible for participation if, and only if, they have comorbidities precluding surgery or refuse to undergo an operation following a multi-disciplinary discussion involving surgical oncology, medical oncology, and radiation oncology. This discussion will actively involve the patient and reinforce that surgery is the current standard of care for such patients.
- g. Cirrhotic status of Child-Pugh class A or B (Appendix I)
- h. Patients can have extra-hepatic disease, provided the hepatic disease is the highest burden, the extra-hepatic disease is low burden and potentially treatable with surgery, ablative radiation therapy, or US Food and Drug Administration—approved first- or second-line systemic therapy regimens.
- i. Patient's will have no evidence of gross vascular invasion.
- j. Patients will have no more than 3 distinct lesions, all being  $\leq$  3cm in greatest dimension, OR 1 lesion  $\leq$  6cm in greatest dimension.
- k. Platelet count  $\geq 60 \times 10^9 / L$ , Hemoglobin  $\geq 8.5 \text{ g/dL}$ , WBC  $\geq 2000 / \mu L$  International normalized ratio (INR) must be  $\leq 2.3$ . Patients who are being therapeutically anticoagulated with an agent such as Coumadin or heparin will be allowed to participate provided that no prior evidence of underlying abnormality in these parameters exists.

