#### 6.5.1.2 Tumor Response on CT (RECIST)

Measurable Disease Response: CTEP's RECIST guidelines will be followed. A quick reference to the RECIST guidelines can be downloaded at the following URL: http://ctep.info.nih.gov/Policies/WordDocs/RCSTF.PH2TEMPF.doc. (Appendix II) Patients enrolled in this study must have a measurable liver metastasis which is defined as lesions that can be accurately measured in at least one dimension: [longest diameter to be recorded] on the CT scan.

The same method of assessment and the same technique should be used to characterize each identified & reported lesion at baseline & during follow-up.

F	Parameters to Measure Response Outcome:			
1 Clinical examination				
2	CT scan			
3	FDG-PET/CT scan			

Taking into account the measurement of the longest diameter only for those lesions with size response, response criteria are defined as:

- 1. Complete Response (CR): the disappearance of a lesion.
- 2. Near Complete Response (NCR): at least an 80% decrease in the longest diameter of a lesion, taking as reference the longest diameter recorded since the treatment started.
- 3. Partial Response (PR): at least a 30% decrease in the longest diameter of a lesion, taking as reference the longest diameter recorded since the treatment started.
- 4. Progressive Disease (PD): at least a 25% increase in the longest diameter of a lesion, taking as reference the longest diameter recorded since the treatment started.
- 5. Stable Disease (SD): neither sufficient shrinkage to qualify for partial response nor sufficient increase to qualify for progressive disease, taking as reference the longest diameter since the treatment started.

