#### 7.0 Statistical Considerations

#### 7.1 Study Design/Endpoints

The primary objective of this study is to determine the Maximum Tolerated Dose (MTD) and safety of SBRT for liver metastasis using dose escalation. Dose escalation will be via the traditional "up and down" scheme indicated in the two tables below. The traditional up and down study design is a rule-based design which recruits up to 6 patients at each of the 3 dose levels. Patients in cohort(s) of 3 will be entered and the first cohort will be given the lowest dose. The detailed decision rule is in the two Tables below, where there are decisions corresponding to one or more dose limiting toxicities at any given dose level.

- The three dose levels are:
  - 50 Gy in 5 fractions (10 Gy/fx) delivered over a 2-week period.
  - 60 Gy in 5 fractions (12 Gy/fx) delivered over a 2-week period.
  - 75 Gy in 5 fractions (15 Gy/fx) delivered over a 2-week period.

Dose limiting toxicity (DLT) will be defined as any grade III stomach, bowel, liver, or spinal cord toxicity, or any grade IV toxicity as defined by the Radiation Therapy Oncology Group (RTOG). The monitoring and evaluation for dose escalation is referenced below in section 7.3.1. Cohorts of three patients each will be treated at a dose level. Only toxicities observed prior to 7 months after the last fraction of radiation will affect dose escalation.

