#### 7.2 Sample Size/Accrual Rate

The number of patients accrued to the study will depend on the MTD. No more than 18 evaluable patients will be treated in the trial. Based on previous efforts in recruiting patients at the University of Pittsburgh Cancer Institute, it is anticipated that at least 6 patients per year will be enrolled in the protocol and the accrual will be completed within 3 years. An evaluable patient is defined as one who either a) completes the five fractions and has no DLT until one month after the last fraction, or b) a patient who receives at least one fraction and suffers DLT. Patients who are not evaluable will be replaced.

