#### Response Criteria

## **Evaluation of target lesions**

* Complete Response (CR):	Disappearance of all target lesions
* Partial Response (PR):	At least a 30% decrease in the sum of the LD of target lesions, taking as reference the baseline sum LD
* Progressive Disease (PD):	At least a 20% increase in the sum of the LD of target lesions, taking as reference the smallest sum LD recorded since the treatment started or the appearance of one or more new lesions
* Stable Disease (SD):	Neither sufficient shrinkage to qualify for PR nor sufficient increase to qualify for PD, taking as reference the smallest sum LD since the treatment started
	Evaluation of non-target lesions

* Complete Response	Disappearance of all non-target lesions and normalization of tumor				
(CR):	marker level				
* Incomplete	Persistence of one or more non-target lesion(s) or/and maintenance of				
Response/	tumor marker level above the normal limits				
Stable Disease (SD):					
* Progressive Disease	Appearance of one or more new lesions and/or unequivocal				
(PD): progression of existing non-target lesions (1)					

(1) Although a clear progression of "non target" lesions only is exceptional, in such circumstances, the opinion of the treating physician should prevail and the progression status should be confirmed later on by the review panel (or study chair).

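### With up to three lesions per patient, conflicting CT rules and no PET combining rule leave patient-level local control and the PET/CT-versus-CT pair undefined, and Section 7.3.2 names no unit for McNemar's test

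*Combined protocol and SAP*

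**What the plan says.** Inclusion criterion 4.3 j reads "Patients will have no more than 3 distinct lesions" (each up to 3 cm), or one lesion up to 6 cm. Four places then bear on how such a patient is scored:

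- **Section 6.5.1.2 (CT)** works on the single lesion. Partial response is "at least a 30% decrease in the longest diameter of a lesion", and progression is a 25% increase in a lesion's longest diameter. It has no step for combining lesions.
- **Appendix II (RECIST)** works on the patient. Partial response is "At least a 30% decrease in the sum of the LD of target lesions, taking as reference the baseline sum LD", and progression is a 20% increase in that sum over its smallest value since treatment started.
- **Section 6.5.1.5** defines local control as sustained stable disease or better in the target lesion(s) at one year, without saying whether all, any or the sum is meant. Local failure is progression anywhere in the target volume. The local response rate is tied to RECIST, with no denominator given.
- **Section 6.5.1.3 (PET)** grades uptake within the tumor region and gives no rule for two or three treated lesions.

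Section 7.3.2 then says "Local control, local failure, regional failure and distant failure of patients, defined in Section 6.5.1.5, will be summarized in tables", with exact 95% intervals, and "The local response rates with FDG-PET/CT will be compared to those with CT using McNemar's test". The unit of that test, its level, and whether it is exact or asymptotic are not stated. Section 7.3 calls the analysis exploratory and mostly by dose group.

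**The concern.** Secondary objectives 2.2 (local control) and 2.3 (PET/CT response against CT) both need one agreed result per unit of analysis. For a patient with two or three lesions, the plan offers two CT rules that can disagree and no PET rule. The choice would fall to whoever builds the tables, possibly after the results are visible.

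Two consequences follow. A patient-level control rate depends on how many lesions the patient had, so dose groups of 3 to 6 patients can differ because of lesion count rather than dose. And because the McNemar sentence has no unit, an analyst could enter each lesion as a separate pair, which the plain test does not allow for when lesions in one patient tend to agree.

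**Working it through.** **Plan's own figure.** "recruits up to 6 patients at each of the 3 dose levels" gives 3 × 6 = 18, which matches "No more than 18 evaluable patients will be treated in the trial" and the accrual of 6 per year × 3 years. The largest possible lesion count is 18 × 3 = 54. No power is stated for the secondary endpoints, so there is none to reproduce.

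**Inputs.** Local control of 71% and 95% at one year comes from the series cited in Section 1.3; treating these as per-lesion rates is an assumption. Lesions per patient in the cited series are 63/47 = 1.34 and 143/70 = 2.04 (the latter "in six fractions in 70 patients with 143 tumors"). The documents give no within-patient correlation (ICC) and no PET–CT discordance, so ranges are used.

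**1. Do the rules conflict?** Take three lesions of 3.0 cm that become 1.5, 1.5 and 4.0 cm and stay there to one year.
- Sum: 9.0 to 7.0 cm, a change of −2.0/9.0 = −22%. Under Appendix II this is stable disease, hence local control.
- Third lesion: +1.0/3.0 = +33%. Under Section 6.5.1.2 this is progression, and under Section 6.5.1.5 it is local failure.

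The patient enters both rates. Even with one lesion, growth of 20% up to just under 25% is progression in Appendix II and stable disease in Section 6.5.1.2.

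**2. Dependence on lesion count.** With per-lesion control p, P(all k controlled) = p^k under independence, and a beta-binomial for ICC 0.5.

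| p | ICC | 1 lesion | 2 lesions | 3 lesions |
|---|---|---|---|---|
| 0.95 | 0 | 95.0% | 90.2% | 85.7% |
| 0.95 | 0.5 | 95.0% | 92.6% | 91.1% |
| 0.71 | 0 | 71.0% | 50.4% | 35.8% |
| 0.71 | 0.5 | 71.0% | 60.7% | 54.8% |

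If any controlled lesion were enough, p = 0.71 with independence gives 71.0/91.6/97.6%, the opposite direction. At ICC 1 there is no dependence.

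For scale, compare two groups of six with average counts close to the two cited series: four patients with 1 lesion and two with 2 (mean 8/6 = 1.33), against two each with 1, 2 and 3 (mean 12/6 = 2.0). Use the all-lesions rule.
- p = 0.71, independent: (4×0.710 + 2×0.504)/6 = 64.1%, against (2×0.710 + 2×0.504 + 2×0.358)/6 = 52.4%. The gap is about 12 points.
- p = 0.71, ICC 0.5: 67.6% against 62.2%, about 5 points.
- p = 0.95, independent: 93.4% against 90.3%, about 3 points.

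**3. McNemar's test.** When all n discordant pairs point one way, exact p = 2 × 0.5^n. Two such patients give 2 × 0.5² = 0.50. If each has three lesions counted separately, 2 × 0.5⁶ = 0.031.

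Simulated type I error at a nominal two-sided 0.05 (18 patients, 100,000 replicates, discordance 0.1, 0.2 or 0.4, no true difference):

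| Unit and lesion mix | ICC | Asymptotic | Exact |
|---|---|---|---|
| Patient, one pair each | – | 0.010–0.045 | 0.000–0.018 |
| Lesion, 3 in all 18 | 0 | 0.043–0.053 | 0.010–0.029 |
| Lesion, 3 in all 18 | 0.2 | 0.088–0.104 | 0.029–0.067 |
| Lesion, 3 in all 18 | 0.5 | 0.156–0.175 | 0.065–0.128 |
| Lesion, 3 in all 18 | 1 | 0.20–0.30 | 0.20–0.25 |
| Lesion, mean 2 | 0.5 | 0.098–0.124 | 0.024–0.087 |
| Lesion, mean 1.44 | 0.5 | 0.052–0.087 | 0.007–0.052 |

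**The case against.** **The plan does not specify a lesion-level test.** A reader might infer that the planned McNemar test ignores clustering and would be falsely significant. The documents do not support that. The same paragraph of Section 7.3.2 speaks of patients, Section 6.5.1.5 ties local response to RECIST, and Appendix II assigns each patient one response category. One pair per patient is the natural reading, and then there is no clustering to ignore. This stands. What remains is that the unit is unstated, and that the pair cannot be formed for a multi-lesion patient without a PET rule and a single CT rule.

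**The documents are not silent on combining lesions.** Appendix II sums diameters, and the local failure definition already works as an any-lesion rule. This also stands: the defect on CT is an unreconciled conflict, not an absence. On PET it is an absence.

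**The extreme figures do not belong together.** The steepest fall with lesion count needs independent lesions. The largest error rates (0.20–0.25, exact test) need lesions in a patient always to agree, and three of them in every patient. Under partial correlation both effects are smaller, and with few lesions per patient the exact test stays near or below 5%.

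**The effect on dose comparison is modest.** No test between doses is planned, and the exact 95% interval for 5 of 6 patients is 36–99.6%. A shift of 3 to 12 points is well inside that noise. This limits the importance of the point, but it does not excuse a rate whose numerator is undefined when exact intervals and a named test are promised.

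**Conclusion.** The point holds as a definitional conflict with a known direction of effect. Sections 6.5.1.2, 6.5.1.5 and Appendix II can classify one multi-lesion patient as both controlled and failed. Patient-level control falls with lesion count under an all-lesions rule and rises under an any-lesion rule, unless lesions within a patient always agree. How far depends on the assumed per-lesion control and ICC. McNemar's test is sound with the patient as the unit; inflation arises only if lesions are entered as independent pairs and are positively correlated within patients. The number of pairs may be below 18, because Sections 6.1.10 and 6.3.3 allow CT-only imaging.

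The change is worth making but not critical: the endpoints are secondary and exploratory, and the MTD decision does not use them.

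**What to change.** 1. **One rule.** Reconcile Sections 6.5.1.2, 6.5.1.5 and Appendix II, including the 25% and 20% progression thresholds and their reference measurements. In Section 7.3.2, define patient-level local control as all treated lesions controlled, so that progression of any treated lesion is local failure. Apply the same combining rule to CT and PET.
2. **PET/CT against CT.** State that the unit is the patient. Use exact McNemar on one pair per patient with both assessments. Report the number of pairs, the paired 2×2 table, and the difference in response rates with a 95% interval for paired proportions.
3. **Supplementary lesion-level results.** Report lesion-level local control and PET-versus-CT agreement with a patient-clustered method, and tabulate lesion count by dose group. Avoid a simple patient bootstrap for the control rate: it has zero width when every lesion is controlled. An exact interval on the design-effect-adjusted sample size does not collapse. With three lesions each, the design effect is 1 + (3 − 1) × ICC, which is 1.4 at ICC 0.2 and 2.0 at 0.5, so 54 lesions count as about 39 or 27. If all 54 were controlled, the lower limit 0.025^(1/n) would be about 91% or 87%, against 93% with n = 54. The ICC cannot be estimated when every lesion is controlled, so the values to be used should be set in advance.

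The cost is wording and a little programming, since lesion measurements are already planned. Lesion-level intervals will be wider than naive ones.

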#### 8.0 Data Safety and Recording

#### 8.1 Data safety monitoring plan

All patient data will be collected by the University of Pittsburgh Cancer Institute's Protocol Office. All data will be secured in a password protected file with observance of all applicable HIPAA regulation. A data safety monitoring board will meet monthly to evaluate toxicity for this trial along with dose escalation and de-escalation. Patients/adverse events will be discussed at these monthly disease center meetings. Unexpected serious adverse events will be reported to the IRB and DSMC, and minutes of the monthly disease center meetings will be reviewed at the DSMC meetings.

#### 8.1.1 Subject Removal Criteria

- 1. Disease progression
- 2. Development of a serious medical illness
- 3. Evidence of dose-limiting toxicity
- 4. Voluntary withdrawal
- 5. Protocol violation
- 6. Discretion of the principal investigator in conjunction with a multi-disciplinary team
- 7. Development of grade 4 toxicity related to experimental therapeutic

## 8.2 Safety Reporting

#### 8.2.1 Acute Adverse Events

The CTCAE (described below) will be used to grade acute toxicity during this trial.

CTCAE term (AE description) and grade: The descriptions and grading scales found in the revised NCI Common Terminology Criteria for Adverse Events (CTCAE) version 4.0 will be utilized for AE reporting. All appropriate treatment areas will have access to a copy of the CTCAE version 4.0. A copy of the CTCAE version 4.0 can be downloaded from the CTEP web site (http://ctep.cancer.gov).

An AE is any untoward medical occurrence in a patient or clinical investigation subject administered a pharmaceutical product that does not necessarily have a causal relationship with this treatment. An AE can therefore be any unfavorable and unintended sign (including an abnormal laboratory finding), symptom, or disease temporally associated with the use of a medicinal (investigational) product, whether or not related to the medicinal (investigational) product.

It may include worsening or increase in severity of signs or symptoms of the illness, increase in frequency of signs and symptoms of an intermittent illness, or the appearance of a new manifestation/complication.

Exacerbation of a pre-existing illness should be considered when a subject requires new or additional concomitant drug or non-drug therapy for the treatment of that illness during the study. Lack of or insufficient clinical response, benefit, efficacy, or therapeutic effect should not be recorded as an adverse event. The investigator must make the distinction between exacerbation of pre-existing illness and lack of therapeutic efficacy.

In addition, abnormal objective test findings (e.g., electrocardiogram changes, abnormal laboratory test results) that can result in a change in study drug dosage or in discontinuation of the drug, or require intervention or diagnostic evaluation to assess the risk to the patient, should also be recorded as adverse events. Clinically significant changes in physical examination findings should also be recorded as adverse events. For all adverse events, the investigator must pursue and obtain information adequate both to determine the outcome of the adverse event and to assess whether it meets the criteria for classification as a serious adverse event requiring immediate notification to UPCI or its designated representative.

**'Expectedness'**: AEs can be 'Unexpected' or 'Expected' for expedited reporting purposes only.

